volume gain with a newly developed collagen matrix was evaluated in chronic ridge defects compared to sub-epithelial connective tissue grafts in dogs. Casts were obtained and soft tissue changes were digitally analyzed. The aim of the current study is to evaluate the soft tissue dimensional changes after extraction of teeth in the esthetic zone, when combined with the placement of implants into these fresh extraction sockets. Furthermore, the effect of placing a graft material, Bio-OSS Collagen®, into the gap between the 3i® implant and the labial plate of bone will be evaluated after an immediately loaded provisional restoration is placed.

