# **Study Design**

This is a single-blind, randomized, controlled, single-center study:

32 subjects will have an immediate implant placed in the maxillary anterior region (#4-12) after extraction of a hopeless tooth. 16 subjects will be randomly selected to receive Bio-Oss Collagen® (Test group) and 16 subjects will have no graft (Control group) in the gap between the implant and the labial plate of bone.

Hopeless maxillary anterior teeth will be extracted and implants will be placed in a flapless procedure. Implants will be immediately loaded with provisional restorations once determined that the implant is stable. Changes in vertical height and horizontal dimensional changes of the free gingival margins will be evaluated at 3, 6, and 12 months post-immediate implant placement. Both groups are only different by the draft that will be placed at the time of implant placement. Both treatment choices are currently standard of care in immediate implant therapy. Patients will only be include into the study if the extraction socket is intact as outlined below and, therefore, immediate implant placement with or without drafting would be possible. If patients decide not to go ahead with the study, treatment could be performed either way in our clinic. Both methods are standard of care.

Based on the literature (see above and here):

Immediate implant placement can be done with or without grafting. An intact socket does not necessarily require grafting. Currently, both procedures (placement with grafting and without grafting) are considered standard of care). One group will receive grafting and the other group

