## **Statistical Procedures**

Our current study aims to analyze dimensional stability after immediate implant placement in fresh extraction sockets. We will simultaneously graft the socket with a synthetic combination bone material and compare it to sockets that will not be grafted. Currently, there are no randomized controlled clinical studies available that compare these two different treatment modalities. However, we will use a randomized controlled study that compared different socket /implant treatments (immediate versus delayed implant placement). They found a difference in buccal/lingual dimensional stability (1.9 in an immediate group versus 3.06 in a delayed group) (Covani et al, 2004). In order to detect a difference of 10% with a power of 80% at a significance level of 0.05 between control and study group, we will need to perform at least 16 procedures per group. Primary efficacy variable is the height and thickness of keratinized tissue at 3,6,12, 24 months post surgery. Post surgery assessment of recession width, color, texture and contour ratings, marginal gingival level, biotype assessment are secondary variables. Summary statistics (mean, SD, median, p25, p75, min, max) will be calculated for all measured variables in each group. Results between both groups will be compared using the Student's t-test for normal distribution and the Mann- Whitney-U test for a non-parametric distribution of values. Categorical values will be compared using the chi-square test. For secondary analyses, we will use appropriate parametric or nonparametric tests to compare group differences.

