# **Study Procedures**

At the present time, grafting or no grafting at the time of implant placement can be considered standard of care. We will take measurements to compare both groups. How measurements are taken is outlined below:

The surgical technique is described as:

- 1. Administration of 2000mg Amoxicillin-1 hour prior to surgery. For patients allergic to Amoxicillin, 600mg Clindamycin 1 hour prior to surgery will be substituted.
- 2. Administration of local anesthesia and impression using alginate will be taken to measure ridge dimensions.
- 3. Extraction of hopeless tooth will be performed without a flap. Dental extractions are usually done without raising a flap. Only if the tooth is very compromised and the tooth is difficult to access, a flap needs to be raised. Extraction sockets will be evaluated to determine whether it is intact and has no lesion or shows signs of bone loss. This can be done using a periodontal probe. Dental implants will only be placed if the socket is intact.
- 4. Check for labial plate of bone that is <4mm from the gingival margin.
- 5. Placement of implant into socket towards palatal wall.
- 6. Measure:
  - a. Thickness of buccal plate 1 mm from crest with special calipers.
  - b. Distance from buccal of implant to buccal crest of bone (horizontal gap distance).
  - c. Vertical depth of gap on facial aspect of implant
  - d. 16 subjects will randomly get Bio-OSS Collagen® packed firmly into gap.
- 7. Place temporary abutment and fabricated screw-retained provisional.
- 8. No sutures will be used since no flap was raised. However, if at the surgeon's discretion sutures were indicated, they will be placed. An X-ray will be taken after implant placement. This is standard of care. However, a half arch alginate impression will be taken and attached to the rim that is being used to hold the X-ray film. This way the patient will always bite down in the same way and the X-ray will always be shot in the same angulation.
- 9. Take 2nd alginate impression:
- 10. Placement of subject on appropriate analgesic (i.e. Acetominophen with or without codeine #3 or #4, or Motrin 600mg, or Vicodin 500/5/1-2 tabs q6h prn. Rinses with 0.12% Chlorhexidine Gluconate BID for 14 days.
- 11. Subject will be seen at 1 week post op.

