- 12. Subject will be seen at 3,6 and 12 months. At each of these visits, alginate impressions will be taken and digitally scanned and analyzed. At 6 months, periapical film will be taken and pick-up impression with open tray impression coping.
- 13. Deliver screw retained final restoration with zirconia framework and pressed lithium disilicate.
- 14. Take 6th alginate impression. At one year (6 months after delivery of final restoration.) Measure Vertical height of free gingival margin from MGJ Visits 1, 2, 4-6. Measure horizontal dimensional change to tenth of mm using calipers 1mm, 2mm below gingival margin at Visits 1, 2, 4-7.

- 15. All models created from alginates will be poured with Whip Mix labstone. All models used for fabrication of the final crown will be poured in silky Rock (Whip Mix) or Resin Rock (Whip Mix).
- 16. Measurements will be done by scanning the facial tissues on each model and then superimposing them on the original one. The difference in height (wKT) and facial-lingual dimension (thickness or tKT) of the free gingival will be evaluated at 3, 6 and 12 months.
- 17. The cast that was used for the final crown will be evaluated for facial thickness of tissue by measuring one mm and 2mm below the margin of the free gingiva.
- 18. Images of the implant crown, the surrounding gum tissue and the neighboring teeth will be shown to people outside of the study and they will be asked to rate the color change of the gum tissue.
- 19. De-identified data will be transferred from Columbia to Jena University. Transfer will be done using an encrypted external device. Data will be stored on a desktop computer at Jena University. The computer is password protected.

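### The primary comparison is unadjusted and does not say whether values or changes are tested; ANCOVA on the pre-extraction measurement would settle this and, in most settings tried, gain precision

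*Combined protocol and SAP*

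**What the plan says.** - **Test.** Statistical Procedures: "Results between both groups will be compared using the Student's t-test for normal distribution", with the Mann-Whitney test for non-normal data. No covariate or adjusted model is named anywhere.
- **Outcome worded as values.** Statistical Procedures: "Primary efficacy variable is the height and thickness of keratinized tissue at 3,6,12, 24 months post surgery".
- **Outcome worded as change.** The aim in Background is to "evaluate the soft tissue dimensional changes after extraction of teeth in the esthetic zone". Study Design: "Changes in vertical height and horizontal dimensional changes of the free gingival margins will be evaluated". Item 16 of Study Procedures gives the method: "Measurements will be done by scanning the facial tissues on each model and then superimposing them on the original one". What is then evaluated is wKT (height) and tKT (thickness), each as a difference.
- **Baseline.** Study Procedures, item 2, before the extraction in item 3: "impression using alginate will be taken to measure ridge dimensions". A second impression follows in item 9, after the graft in item 6d. Item 14 adds "Measure Vertical height of free gingival margin from MGJ Visits 1, 2, 4-6" and "Measure horizontal dimensional change to tenth of mm using calipers 1mm, 2mm below gingival margin at Visits 1, 2, 4-7", but visit numbers are not mapped to time points.

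**The concern.** Two things are left open. The first is which quantity enters the test. A follow-up value and a change from baseline, taken from the same patients, have different variances and can give different p-values. With both wordings in the document, an analyst could defend either after seeing the data.

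The second is that a pre-extraction record is made for every patient and the analysis makes no use of it as a covariate. With 16 patients per group, precision is scarce. ANCOVA with the baseline of the same dimension deals with both matters, because its treatment estimate does not depend on whether the outcome is entered as a value or as a change.

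**Working it through.** **Inputs from the documents.** 16 + 16 = 32 patients; significance level 0.05 (two-sided assumed); power 80%. The stated 16 per group cannot be reproduced, because no SD is given. What can be said is that an unadjusted t-test with 16 per group has 80% power for a difference of 1.02 SD of whatever quantity is tested (noncentral t, 30 df).

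**Assumed, not in the documents.** Baseline/follow-up correlation r = 0.3, 0.5, 0.7, 0.8; follow-up SD = k × baseline SD, with k = 0.8, 1, 1.25.

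**Formulas**, as variance relative to a t-test on follow-up values:

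- follow-up value: 1
- change: 1 + 1/k² − 2r/k
- ANCOVA: (1 − r²) × [1 + 1/(32 − 4)] = (1 − r²) × 29/28, with 29 error df. The factor 29/28 = 1.036 is the expected cost of estimating the covariate slope.

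**Example**, r = 0.5 and k = 1: change = 1 + 1 − 1 = 1.000; ANCOVA = 0.75 × 29/28 = 0.777; cut = 22.3%.

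**Average variance cut by ANCOVA, net of the covariate cost:**

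| Compared with | r = 0.3 | 0.5 | 0.7 | 0.8 |
|---|---|---|---|---|
| Change, k = 1 | 32.7% | 22.3% | 12.0% | 6.8% |
| Change, k = 0.8 | 48.0% | 40.8% | 35.0% | 33.7% |
| Change, k = 1.25 | 18.8% | 7.5% | −1.6% | −3.6% |
| Follow-up value, any k | 5.7% | 22.3% | 47.2% | 62.7% |

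The first three rows apply if change is intended, the last row only if follow-up values are. Against change, ANCOVA gains for r below 0.93 if k = 1 and at every r if k = 0.8. If k = 1.25 it loses slightly for r between about 0.66 and 0.89.

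**Detectable difference at 80% power, k = 1, in follow-up SDs:**

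| Test | r = 0.3 | 0.5 | 0.7 | 0.8 |
|---|---|---|---|---|
| Change | 1.21 | 1.02 | 0.79 | 0.65 |
| ANCOVA | 1.00 | 0.90 | 0.75 | 0.63 |
| Follow-up value | 1.02 | 1.02 | 1.02 | 1.02 |

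**Covariate cost.** 1/(N − 4) is 3.6% with N = 32, 4.2% with 28, 4.5% with 26 and 5.0% with 24. These are averages over randomisations. In simulation with all 32 analysed, the 95th percentile of the factor in a single trial was about 1.14, reached when the arms differ by chance at baseline.

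**Open choice.** In simulation with no true difference, each single test rejected in about 5% of trials. Follow-up value or change (either one) was significant in about 8–10%.

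**Displacement only.** If tKT exists only as displacement from the superimposed model, the cut is 1 − (1 − ρ²) × 29/28, where ρ is its correlation with the absolute baseline dimension: −3.6% at ρ = 0, 5.7% at |ρ| = 0.3, 22.3% at |ρ| = 0.5.

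**The case against.** The strongest reply is that the documents point to change. Item 16 defines both dimensions by superimposing models and taking the difference, and Background and Study Design speak of changes. Statistical Procedures opens with dimensional stability and takes its benchmark from it. The one sentence worded as values may only be naming the variable and its visits. On that reading the gain is the versus-change one, which is small at high correlation and can be a slight loss. This largely stands, and it is why those figures lead here. It does not supply the missing sentence saying what is tested, or from which cast change is measured.

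Three stronger readings are tempting and not supported:

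- **That the planned tests are biased or invalid.** Under randomisation an unadjusted comparison of either quantity is valid.
- **That the false-positive rate will be 8–10%.** That requires both quantities to be tested and the better one reported. The plan does not say this will be done; it only fails to rule it out.
- **That ANCOVA can never lose more than about 4%.** The 3.6% is an average, in variance, with all 32 analysed.

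A further objection is that item 14 is weak evidence of a baseline. Equating Visit 1 with pre-extraction is an inference, and its horizontal reading is worded as a change, at levels below a margin that can itself move. That is right, so the baseline should rest on the item 2 cast.

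**Conclusion.** The point holds as an underspecified analysis and a cheap gain in efficiency, not as an error of validity. The tested quantity is not stated, though change is probably intended, and no baseline covariate is named although a pre-extraction cast exists. Against a change-score t-test, the average variance reduction ranges from 48% to a loss of about 4% over the assumed r of 0.3–0.8 and k of 0.8–1.25; ten of the twelve settings are gains. If follow-up values were meant, it is 6% to 63%. The size depends on r and k, which the documents do not give, and on all 32 patients being analysed.

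**What to change.** State in Statistical Procedures that:

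- wKT and tKT at each planned visit are compared by ANCOVA, with treatment and the pre-extraction value of the same dimension as terms, reporting the adjusted difference with its 95% CI;
- the reference is the item 2 cast, not the post-graft impression of item 9;
- the tKT covariate is the absolute facial-lingual dimension on the item 2 cast, at a level fixed on that cast, because displacement is zero at baseline for everyone;
- if tKT exists only as scan displacement, displacement is the outcome and that same absolute dimension the covariate;
- Mann-Whitney on change is kept as the sensitivity analysis for non-normal data.

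The cost is SAP wording, one absolute reading per patient on a cast already made, one degree of freedom, and the average variance cost of 3.6% (4–5% with 24–28 analysed, and more in a single trial with a large chance baseline imbalance). No extra visit or patient procedure is needed. Choosing a single primary visit, and multiplicity across wKT and tKT, are separate issues that this change does not settle.

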## **Confidentiality of Study Data**

Confidentiality of Study Data Patients will receive a study number that corresponds the medical record number. Notes and evaluation results during the visits will be recorded electronically or on paper. All paper information will be entered into a Microsoft Excel database for storage and/or stored in a locked cabinet. All consent forms, after being 09/18/2015 signed by the patient and the study documentations will be kept in a locked cabinet in the principal investigator's office. Besides the personnel involved in the study, the following parties may review or copy consent forms, dental records or study documentation: The sponsor and their designees; Agents of the FDA; CUMC and OHRP. Because of the need to release information to these parties, absolute confidentiality cannot be guaranteed. Furthermore, the aggregate results of this study may be used for teaching purposes, at meeting, or in publications, the subject's identity will not be disclosed in these presentations. Electronic data will be stored on encrypted end user devices.

# **Study Procedures**

At the present time, grafting or no grafting at the time of implant placement can be considered standard of care. We will take measurements to compare both groups. How measurements are taken is outlined below:

The surgical technique is described as:

- 1. Administration of 2000mg Amoxicillin-1 hour prior to surgery. For patients allergic to Amoxicillin, 600mg Clindamycin 1 hour prior to surgery will be substituted.
- 2. Administration of local anesthesia and impression using alginate will be taken to measure ridge dimensions.
- 3. Extraction of hopeless tooth will be performed without a flap. Dental extractions are usually done without raising a flap. Only if the tooth is very compromised and the tooth is difficult to access, a flap needs to be raised. Extraction sockets will be evaluated to determine whether it is intact and has no lesion or shows signs of bone loss. This can be done using a periodontal probe. Dental implants will only be placed if the socket is intact.
- 4. Check for labial plate of bone that is <4mm from the gingival margin.
- 5. Placement of implant into socket towards palatal wall.
- 6. Measure:
  - a. Thickness of buccal plate 1 mm from crest with special calipers.
  - b. Distance from buccal of implant to buccal crest of bone (horizontal gap distance).
  - c. Vertical depth of gap on facial aspect of implant
  - d. 16 subjects will randomly get Bio-OSS Collagen® packed firmly into gap.
- 7. Place temporary abutment and fabricated screw-retained provisional.
- 8. No sutures will be used since no flap was raised. However, if at the surgeon's discretion sutures were indicated, they will be placed. An X-ray will be taken after implant placement. This is standard of care. However, a half arch alginate impression will be taken and attached to the rim that is being used to hold the X-ray film. This way the patient will always bite down in the same way and the X-ray will always be shot in the same angulation.
- 9. Take 2nd alginate impression:
- 10. Placement of subject on appropriate analgesic (i.e. Acetominophen with or without codeine #3 or #4, or Motrin 600mg, or Vicodin 500/5/1-2 tabs q6h prn. Rinses with 0.12% Chlorhexidine Gluconate BID for 14 days.
- 11. Subject will be seen at 1 week post op.
- 12. Subject will be seen at 3,6 and 12 months. At each of these visits, alginate impressions will be taken and digitally scanned and analyzed. At 6 months, periapical film will be taken and pick-up impression with open tray impression coping.
- 13. Deliver screw retained final restoration with zirconia framework and pressed lithium disilicate.
- 14. Take 6th alginate impression. At one year (6 months after delivery of final restoration.) Measure Vertical height of free gingival margin from MGJ Visits 1, 2, 4-6. Measure horizontal dimensional change to tenth of mm using calipers 1mm, 2mm below gingival margin at Visits 1, 2, 4-7.

- 15. All models created from alginates will be poured with Whip Mix labstone. All models used for fabrication of the final crown will be poured in silky Rock (Whip Mix) or Resin Rock (Whip Mix).
- 16. Measurements will be done by scanning the facial tissues on each model and then superimposing them on the original one. The difference in height (wKT) and facial-lingual dimension (thickness or tKT) of the free gingival will be evaluated at 3, 6 and 12 months.
- 17. The cast that was used for the final crown will be evaluated for facial thickness of tissue by measuring one mm and 2mm below the margin of the free gingiva.
- 18. Images of the implant crown, the surrounding gum tissue and the neighboring teeth will be shown to people outside of the study and they will be asked to rate the color change of the gum tissue.
- 19. De-identified data will be transferred from Columbia to Jena University. Transfer will be done using an encrypted external device. Data will be stored on a desktop computer at Jena University. The computer is password protected.

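### The only pre-extraction impression is listed after local anesthesia, so temporary facial swelling could be counted as tissue loss in both arms

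*Combined protocol and SAP*

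**What the plan says.** The numbered surgical sequence in Study Procedures puts anesthesia and the first impression into one step, item 2, ahead of the extraction in item 3: "Administration of local anesthesia and impression using alginate will be taken to measure ridge dimensions". After the implant and provisional are in place, item 9 says "Take 2 nd alginate impression". For the visits at 3, 6 and 12 months, item 12 says "At each of these visits, alginate impressions will be taken and digitally scanned and analyzed" and mentions no anesthesia.

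Item 16 defines the measurement: "Measurements will be done by scanning the facial tissues on each model and then superimposing them on the original one". It continues: "The difference in height (wKT) and facial-lingual dimension (thickness or tKT) of the free gingival will be evaluated at 3, 6 and 12 months". Item 14 adds caliper readings: "Measure horizontal dimensional change to tenth of mm using calipers 1mm, 2mm below gingival margin at Visits 1, 2, 4-7".

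Statistical Procedures names the outcome: "Primary efficacy variable is the height and thickness of keratinized tissue at 3,6,12, 24 months post surgery". Background puts the description of change first, "The aim of the current study is to evaluate the soft tissue dimensional changes after extraction of teeth in the esthetic zone", and then adds the effect of the graft.

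The documents do not state the injection site or volume, a waiting time before the impression, which cast is the original one, or any correction for swelling.

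**The concern.** A change score is only as good as its reference. If the reference cast records tissue distended by anesthetic and the later casts do not, the distension disappears by the first follow-up and is read as shrinkage. Randomisation does not help the within-arm estimates, because every subject in both arms has the same baseline step. Background calls soft-tissue change poorly documented, so the absolute amount of change in each arm is a result that readers will use. It cannot be repaired later: the tooth is extracted in the next step, and the pre-extraction state cannot be recorded again.

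**Working it through.** **Which cast is the reference?** Item 9 numbers its impression as the second, so one impression precedes it, and item 2 is the only one described. The item 2 cast is therefore the natural original model. The item 9 cast comes from the same visit, after anesthesia, extraction and implant placement. Choosing it as the reference would not clearly avoid the problem, and it would not show the pre-extraction state.

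**Effect on the change score.** For one subject let T be the true baseline dimension, B the swelling at the baseline impression and F the follow-up dimension.

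- Measured change = F − (T + B) = true change − B.
- Within an arm, mean measured change = mean true change − m, where m is mean swelling.
- Between arms, (graft − m) − (control − m) = graft − control, so m cancels.
- Between two follow-ups, for example 3 to 12 months, B also cancels.

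A simulation of 40,000 trials with 16 per arm, no true arm difference, an assumed true change of −0.6 mm and an assumed SD of 0.3 mm agrees:

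| Assumed swelling, mean (SD), mm | Mean measured change in an arm, mm | Arm difference, mm | Type I error |
|---|---|---|---|
| 0 (0) | −0.6 | 0.0011 | 4.9% |
| 0.2 (0.1) | −0.8 | 0.0002 | 5.1% |
| 0.5 (0.2) | −1.1 | 0.0002 | 5.1% |
| 1.0 (0.3) | −1.6 | 0.0001 | 5.0% |

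The swelling values are assumptions, chosen to show the mechanism.

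**Noise, as an illustration only.** Statistical Procedures states 16 per group for a 10% difference, 80% power and a 0.05 significance level. That figure cannot be reproduced, because no SD is given and the base of the 10% is not defined. Working backwards with the two-sided normal approximation, SD = difference × √(16/2) / (1.960 + 0.842):

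- 10% of 1.9 = 0.19, implied SD 0.192
- 10% of 3.06 = 0.306, implied SD 0.309
- 3.06 − 1.9 = 1.16, implied SD 1.171

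If swelling is independent of the true change and has SD s, the change-score SD becomes √(SD² + s²). Power at 16 per arm, treating the planning values as mm (the plan gives no unit):

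| Difference | s = 0 | s = 0.1 | s = 0.2 |
|---|---|---|---|
| 0.19 | 80% | 70% | 49% |
| 0.306 | 80% | 76% | 65% |
| 1.16 | 80% | 80% | 79% |

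The result depends almost wholly on which difference is meant and on s, and the documents settle neither. If swelling lay between an assumed 0.1 and 0.5 mm, the largest possible SD would be (0.5 − 0.1)/2 = 0.2, with half the subjects at each end. An even spread would give 0.4/√12 ≈ 0.115. The last column is therefore an extreme case.

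**The case against.** The strongest reply is that the order is not firmly stated. Item 2 joins two tasks with 'and' and never says that one follows the other. Item 14 refers to Visits 1, 2 and 4 onward without a visit table, and Visit 1 could be a separate pre-surgical visit. This stands in part: the sequence is by listing only, and the remedy should not assume that Visit 1 is the day of surgery. It does not remove the point. No impression is described at an earlier visit, and item 9's numbering leaves room for only one before it.

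A second reply is that Statistical Procedures names height and thickness at each time point, not change from baseline, and specifies between-group tests. If follow-up values are compared directly, baseline swelling does not enter the test. That is correct for the between-group test. It does not protect the differences against the original model in item 16, or the stated aim.

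A third reply is that the effect may be small where it is measured. The caliper readings are 1 and 2 mm below the margin, where swelling may be less than further apically, and an effect on height is less certain than one on thickness. This also stands, and the documents cannot settle it.

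A reader might want to express the artefact as a share of the 0.6 mm displacement cited in Background. The documents do not support that. The 0.6 mm is an apical, vertical movement from a two-stage procedure, whereas the swelling at issue is mainly in facial thickness, and item 16 treats the two as separate outcomes.

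**Conclusion.** The point holds as a measurement flaw of unknown size. Followed as listed, the plan takes its likely reference cast in anesthetised tissue and its follow-up casts without listed anesthesia. Mean swelling would inflate apparent loss by its full amount in both arms, chiefly in thickness, and variable swelling would add some noise to change scores.

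This rests on three assumptions: the listed order is followed, the item 2 cast is the original one, and the anesthetic distends the scanned facial tissue at the time of the impression. The last is not in the documents.

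A reader might infer that the graft comparison is biased. It is not: the step is the same in both arms and precedes grafting. A reader might also infer that the trial is materially underpowered for this reason. The documents do not show that: the loss ranges from about 1 point (difference 1.16) to about 31 points (difference 0.19) at the extreme s = 0.2, and every input SD is back-solved or assumed.

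**What to change.** In item 2, take the baseline alginate impression, and any baseline caliper readings made that day, before local anesthetic is given. In item 16, state that this pre-anesthetic, pre-extraction cast is the original model for all superimpositions. If the impression is already taken first in practice, the same wording serves as a clarification. The cost is the reordering of two same-day steps, with no added visit or procedure.

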Whether complete bone fill may occur, regardless of the size of the gap distance between the buccal plate and implant, is still a question to be answered. Botticelli et al. (2004) found that marginal gaps of 3.4 mm can heal with substantial bone formation without the use of barrier membranes or filler materials. Also, a convex surface such as a properly designed provisional restoration provides a template against which soft tissue can heal and remodel (Weinlander, 2010). Ideally, it will allow for adequate bulk of tissue formation and proper emergence profile while meeting esthetic demands and protecting any graft material placed in the gap. Studies have also addressed the effect of gingival biotype on hard and soft issues in immediate extraction implant procedures in the esthetic zone (Kois, 2001, Kan, 2011). Kan (2011) reported apicoocclusal facial gingival tissue stability following immediate implant placement in the maxillary esthetic zone without guided bone regeneration, favorable success rates and periimplant tissue responses. Although this study reported spontaneous interproximal papilla regeneration, there was however, continued overall facial recession, more so in the thin soft tissue biotype than the thick tissue biotype. Raes at el. (2011) reported successful results and less vertical recession of the facial gingival with a flapless surgical approach during immediate implant placement in thick biotype cases where the bony walls are intact and proper treatment planning with diagnostic tools is executed in appropriate cases. It is a challenge to measure changes in soft tissue width because this dimension is difficult to assess and reproduce. Windlisch et al. (2007) described a new method to measure intra-oral volume changes based upon an optical system which scans the intraoral anatomy with a camera (Schneider, 2003.) In an in vitro study, several datasets of 3-D objects were captured and volumetric differences measured. The results were highly accurate and reproducible. The same method was reported by Strebel et al. (2009) and Schneider et al. (2010) to measure soft tissue changes of the dental papilla, alveolar ridge and buccal mucosa. In a recent study by Thoma et al. (2010), soft tissue

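### Buccal plate thickness and gap dimensions are recorded before the graft step in all subjects but enter no between-group comparison; one should be a prespecified covariate

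*Combined protocol and SAP*

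**What the plan says.** Study Procedures, item 6, lists four steps. Steps a to c measure the thickness of the buccal plate, the horizontal gap ("Distance from buccal of implant to buccal crest of bone (horizontal gap distance") and the vertical depth of the gap. Step d packs graft into the gap in the 16 subjects randomised to it. Steps a to c are not limited to either arm.

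Statistical Procedures names height and thickness of keratinized tissue as the primary variable and lists the secondary variables. The three site readings are in neither list. The section promises summary statistics by group for all measured variables, which covers these readings. On inference it states: "Results between both groups will be compared using the Student's t-test for normal distribution", with Mann-Whitney as the non-parametric alternative, chi-square for categorical data, and suitable tests of group differences for secondary analyses. It names no covariate, stratification factor, subgroup or interaction. The sample size statement is "we will need to perform at least 16 procedures per group".

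The Background says that buccal bone loss is the more pronounced after extraction and that ridge changes have to be considered when immediate implants are placed. On bone fill, it says that whether this is complete "regardless of the size of the gap distance between the buccal plate and implant, is still a question to be answered".

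**The concern.** The graft is placed in the gap between implant and labial plate. The width and depth of that gap and the thickness of the plate beside it are plausible predictors of how the overlying tissue changes. The trial measures all three, and in the listed order they come before the intervention, so they could serve as baseline covariates.

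With 16 per arm, any explained variance is worth having. If a reading predicts the outcome, an unadjusted test leaves that variation in the error term and gives a wider interval for the graft effect than the same data could support. The choice has to be made in advance: a covariate added after the data are seen is open to challenge as selective.

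**Working it through.** **Inputs from the plan.** 16 per group, 1:1; 80% power and significance level 0.05 ("with a power of 80% at a significance level of 0.05 between control and study group"). Sidedness is not stated; two-sided is assumed.

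**Inputs that are assumptions.** R² is not in the documents and is varied from 0 to 0.3. No SD is given either, so effects are in SD units.

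**Step 1: the plan's own figure.** Statistical Procedures gives a target ("In order to detect a difference of 10" percent) and reference values ("1.9 in an immediate group versus 3.06 in a delayed group"), but no SD, so 16 per group cannot be reproduced. It can be solved backwards. With noncentrality d·√(n/2), n = 16 and 30 degrees of freedom, 80% power requires d = 1.02 (check: 1.0237 × √8 = 2.895, critical t = 2.042, power 0.800). The implied SD is 0.19/1.02 = 0.19 if the target is 10% of 1.9, 0.306/1.02 = 0.30 if it is 10% of 3.06, and 1.16/1.02 = 1.13 for the full difference. None of these SDs is stated. The 80% starting point below is therefore conditional on the effect really being 1.02 SD.

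**Step 2: power after adjustment.** With k covariates:
- residual variance is multiplied by (1 − R²);
- chance imbalance in the covariates inflates the variance of the treatment estimate by about 1 + k/(2n − 3 − k), which is 1 + 1/28 = 1.036 for k = 1 and 1 + 2/27 = 1.074 for k = 2;
- degrees of freedom are 30 − k;
- noncentrality is 2.895/√[(1 − R²) × inflation].

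Example, k = 1 and R² = 0.2: 2.895/√(0.8 × 1.036) = 3.18 on 29 df, power 0.867.

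| Assumed R² | No covariate | One covariate | Two covariates |
|---|---|---|---|
| 0 | 0.80 | 0.785 | 0.77 |
| 0.1 | 0.80 | 0.83 | 0.81 |
| 0.2 | 0.80 | 0.87 | 0.85 |
| 0.3 | 0.80 | 0.91 | 0.90 |

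Adjusted power equals 0.80 at R² of about 0.04 for one covariate and about 0.07 for two. A simulation with one covariate, in which the covariate is left to fall unevenly by chance, gave 0.785, 0.83, 0.865 and 0.91. With all three readings it gave 0.75, 0.80, 0.85 and 0.89, so using all three is the least efficient option.

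**Step 3: a graft-by-gap interaction.** A simulated regression with 32 subjects and an interaction term gave power of about 10%, 24%, 47%, 70% and 84% for slope differences of 0.25, 0.5, 0.75, 1.0 and 1.2 residual SD per SD of gap. Splitting at the median gap, an interaction as large as the main effect has power Φ(0.99/√(4/8) − 1.96) = Φ(−0.56), or about 29%.

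**The case against.** The strongest reply is that the unadjusted test is valid. Under randomisation, chance imbalance in gap or plate thickness is already allowed for in the test's error rate, and the by-group summary would show it. Adjustment is an efficiency choice, and with R² below about 0.04 (one covariate) or 0.07 (two) it costs a little power. The documents offer no correlation between these readings and the outcome. All of this stands, and it is why the point is conditional.

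It is also fair to say that list order alone does not make the readings pre-treatment. The plan does not say when the arm is disclosed; if the operator knows it beforehand, the readings could be influenced. The fix has to deal with that.

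A reader might infer four stronger points that the documents do not support:
- *The readings are not used at all.* They are, descriptively, in the summary of all measured variables.
- *The trial leaves its own gap-size question unanswered.* The Background sentence concerns bone fill. The stated aim is soft tissue change and the effect of grafting, and gap size is not a study objective.
- *A prespecified interaction would show whether the graft effect depends on the gap.* With 32 subjects it would rarely do so.
- *Subjects without a fillable gap dilute the graft arm.* The Background says that marginal defects usually exist after such placement, no share of no-gap subjects is given, and the exclusion criteria are not in the text available, so the absence of a gap requirement cannot be established.

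**Conclusion.** The point holds in a limited form. Three site readings are taken in all subjects, are listed before the graft step, and have no role in any between-group comparison. This does not bias the planned test. The plan forgoes precision if the readings predict soft tissue change: about 3 points of power at R² = 0.1 and 11 at R² = 0.3 with one covariate, against a loss of about 1.5 points if it explains nothing. With two covariates the figures are gains of about 1 and 10 points against a loss of about 3. These results assume a two-sided 0.05 test, a true effect of 1.02 SD, complete data on 16 per arm and a roughly linear relation between covariate and outcome. The bounded loss and the low break-even make prespecified adjustment a reasonable choice, but the gain itself cannot be confirmed from the documents.

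**What to change.** In Statistical Procedures, replace the unadjusted primary comparison with a prespecified ANCOVA that has treatment arm and horizontal gap (item 6b) as fixed terms. Buccal plate thickness (item 6a) may be added as a second covariate; if so, commit to it in advance. Keep the t-test or Mann-Whitney test as a sensitivity analysis.

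In Study Procedures, state that readings 6a to 6c are recorded before the arm is disclosed.

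If a graft-by-gap term is wanted, label it exploratory and report the estimate with its confidence interval, without drawing a conclusion from the p-value.

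The cost is a change from a two-sample test to a linear model in the analysis text and one sentence on the order of recording. No new measurements are needed. The statistical price is about 1.5 points of power with one covariate, or 3 with two, if they prove uninformative.
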